**(3) Study endpoint:**

**① Primary end point:** progression of DKD. Progression of DKD was defined as renal failure (requiring transplantation or dialysis, or persistent eGFR <15 ml/min/1.73 m^2) or a persistent decline of 30% in eGFR from baseline.

**② Secondary End Points:** I. Cardiogenic Death: Death caused by cardiac disease or related complications. II. Major Adverse Cardiovascular Events (MACE): Including myocardial infarction, stroke, unstable angina pectoris, and other significant cardiovascular events. III. Kidney Transplantation: Successful cases of kidney transplantation surgery. IV. Hypoglycemic Events: Documentation of the frequency and severity of hypoglycemia occurrences.

**(4) Specific objectives:** I. Evaluate the relationship between GV and prognosis in patients with DKD and determine the optimal GV control target. II. Screen for biomarkers of gut microbiota, metabolites, and inflammatory factors associated with DKD prognosis.

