### 4.2 Innovativeness

(1) Multidimensional assessment: On one hand, continuous glucose monitoring (CGM) technology is employed to dynamically track glycemic variability in diabetic kidney disease (DKD) patients, capturing detailed fluctuations in blood glucose levels. On the other hand, integrated analysis combines 16S rRNA high-throughput sequencing with serum non-targeted LC-MS to comprehensively evaluate gut microbiota composition and serum metabolite profiles, thereby elucidating their correlations with glycemic variability and disease prognosis.

(2) DESIGN OF PROSPECTIVE COHORT STUDY: A prospective cohort study was designed to enroll patients with different clinical stages of DKD and follow up for 3 years. Adverse prognostic events during follow-up were recorded in detail to ensure the continuity and integrity of the collected data, which provided a strong guarantee for the accuracy and reliability of the study results.

(3) multilevel data integration: the multilevel data, including glycemic variability, clinical indicators, gut microbiota, serum metabolites and inflammatory factors, were integrated to construct a predictive model for DKD prediction.

The risk of adverse prognostic events provides a more comprehensive and accurate tool for clinical risk assessment.

[figure not shown]

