### 5.3 Study Site and Study Population

**5.3.1 Study site:** From July 1, 2025 to December 31, 2025, the subjects were recruited in the inpatient department of endocrinology department of the Eighth Affiliated Hospital of Sun Yat-sen University according to the inclusion and exclusion criteria.

**5.3.2 Study population:** patients with type 2 diabetes and chronic kidney disease (DKD) (n=270)

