## 5.4 Methods for Determining the Required Sample Size for Research

This exploratory study investigates the impact of gut microbiota and related metabolites on prognosis in diabetic kidney disease (DKD) patients. To achieve this, patients will be divided into two groups based on adverse prognosis outcomes, with subsequent comparisons of gut microbiota and metabolite differences between groups. To minimize microbial variations caused by individual differences, each group requires at least 30 participants, meaning there must be at least 30 patients with adverse prognosis events. Drawing from existing research, a 2023 study published in *\*Diabetes Care\** [Diabetes Care.2023;46(4):868-873.] included 975 DKD patients with an average follow-up of 4.7 years, reporting 156 major outcomes of DKD progression. Consequently, the total sample size was calculated as  $975/156*30=187.5$ . Considering potential dropouts and incomplete responses, we typically increase the sample size by 10%, ultimately enrolling 210 patients as the modeling cohort. Additionally, 60 DKD patients were included as a validation cohort. During actual recruitment, sample size adjustments may be made based on factors such as recruitment speed and data quality. Regular assessments of sample adequacy should also be conducted to ensure statistical power.

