### (3) Follow-up in the Queue:

- 1) follow-up time: 3 years after discharge.
- 2) Follow-up methods: outpatient follow-up, telephone follow-up and review of relevant medical records.
- 3) Outcome measures:

**① Primary end point:** progression of DKD. Progression of DKD was defined as renal failure (requiring transplantation or dialysis, or persistent eGFR <15 ml/min/1.73 m^2) or a persistent decline of 30% in eGFR from baseline.

**② Secondary End Points:** I. Cardiogenic Death: Death caused by cardiac disease or related complications. II. Major Adverse Cardiovascular Events (MACE): Including major cardiovascular events such as myocardial infarction, stroke, and unstable angina. III. Kidney Transplantation: Successful cases of kidney transplantation surgery. IV. Hypoglycemic Events: Record the frequency and severity of hypoglycemia occurrences.

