#### **(4) 16S RNA Sequencing Analysis and Non-Target Metabolic Analysis**

We performed 16S rRNA sequencing, non-target metabolic analysis, and inflammatory factor detection on collected fecal and blood samples to compare differences in gut microbiota, metabolites, and inflammatory factors across different prognostic groups, and to identify prognostic markers. We also compared the differences in gut microbiota, metabolites, and inflammatory factors among patients with high glycemic variability, intermediate glycemic variability, and low glycemic variability. Furthermore, we identified gut microbiota markers and serum metabolic markers associated with high glycemic variability.

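### Section 5.4 applies a 4.7-year progression proportion unchanged to a 3-year cohort, so about 20 DKD-progression events are expected, not the 30 the calculation targets

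*Protocol*

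**What the plan says.** Protocol section 5.4 plans to split patients by outcome and compare microbiota and metabolites between the two groups. It states that "each group requires at least 30 participants, meaning there must be at least 30 patients with adverse prognosis events". For the event rate it relies on one published cohort, which "included 975 DKD patients with an average follow-up of 4.7 years, reporting 156 major outcomes of DKD progression". From these it computes 975/156*30 = 187.5, allows about 10% for dropout and incomplete responses, and arrives at 210 for the modelling cohort. A further 60 patients form a separate validation cohort.

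Follow-up is 3 years wherever the protocol states it. Section 4.2 says the study will "enroll patients with different clinical stages of DKD and follow up for 3 years", and section 5.5(3) gives "follow-up time: 3 years after discharge". The last visit in the section 5.6 schedule and the data-collection times in 5.8.1.1 agree.

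The primary end point in sections 3.1(3) and 5.5(3) is progression of DKD ("Progression of DKD was defined as renal failure", or a persistent 30% fall in eGFR). Section 5.4 adds that "sample size adjustments may be made based on factors such as recruitment speed and data quality", and that sample adequacy should be assessed regularly.

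**The concern.** The formula 30 ÷ (156/975) gives the number of patients needed for 30 events only if those patients are followed as long as the cited cohort was. They are followed for 3/4.7 = 64% of that time. Section 5.4 does not convert the proportion and gives no reason to expect faster progression here.

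Thirty patients with an adverse outcome is the only stated basis for 210. That group is also one side of the analysis in section 5.5(4), which is to "compare differences in gut microbiota, metabolites, and inflammatory factors across different prognostic groups". If the group is nearer 20, the comparison is less precise than planned, and the stated minimum is unlikely to be met for the end point whose rate was used.

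**Working it through.** **Inputs (Protocol 5.4, with follow-up from 4.2 and 5.5(3)).** Cited cohort: 975 patients, 156 progression outcomes, mean 4.7 years. Target: 30 events. Enrolled: 210. Follow-up: 3 years. Evaluable: 210 × 0.9 = 189 (derived; the protocol does not state it).

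**Reproducing the protocol's figure.** 156/975 = 0.16 and 30/0.16 = 187.5. The allowance gives 187.5 × 1.1 = 206 or 187.5/0.9 = 208, so 210 is a reasonable rounding.

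**Converting to 3 years.** Three versions:

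- Person-time: 156/(975 × 4.7) = 0.0340 per year; 1 − exp(−3 × 0.0340) = 9.7%.
- Linear: 0.16 × 3/4.7 = 10.2%.
- Exponential, 16% at 4.7 years: −ln(0.84)/4.7 = 0.0371 per year; 1 − exp(−3 × 0.0371) = 10.5%.

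| 3-year risk | Expected in 189 | P(≥30) | Expected in 210 | P(≥30) |
|---|---|---|---|---|
| 9.7% | 18.3 | 0.5% | 20.4 | 2.1% |
| 10.2% | 19.3 | 1.0% | 21.5 | 3.8% |
| 10.5% | 19.9 | 1.5% | 22.1 | 5.3% |
| 16% (as used in 5.4) | 30.2 | 55% | 33.6 | 78% |

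The last row is the comparator: section 5.4 plans on an expected count, so even at a true 16% the minimum of 30 would be far from certain.

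**Sensitivity.**

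- Sampling error in 156/975: the Wilson 95% interval is 13.8–18.4%. The upper limit gives a 3-year risk of 12.2%, hence 23.0 events in 189 or 25.6 in 210. Carrying this uncertainty through raises P(≥30) only to 0.8–2.2% (189) or 2.9–6.7% (210).
- Non-constant hazard: Weibull with H(3) = −ln(0.84) × (3/4.7)^k, where the range of k is my assumption. At k = 0.5 (front-loaded), 24.6 or 27.3 events, with P(≥30) 14% or 32%. At k = 1.5, 16.1 or 17.9 events.
- Half follow-up credit for the 21 dropouts: about 19–21 events.
- All 270 patients pooled: 26–28 events.

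**What 30 would require.** A 3-year risk of 30/189 = 15.9% or 30/210 = 14.3%. That is a hazard 1.55–1.69 times (189) or 1.39–1.51 times (210) the cited one, or about 8–12 further patients with some other adverse event.

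**Effect on precision.** The ratio of standard errors for a between-group difference is √(1/e + 1/(n−e)) ÷ √(1/30 + 1/(n−30)), with e the expected events. It is 1.19–1.23 for n = 189 and 1.14–1.18 for n = 210. The protocol states no power, so this is a precision ratio only.

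**Could the adjustment sentence catch this?** Section 5.3.1 sets the period: "From July 1, 2025 to December 31, 2025, the subjects were recruited". With uniform entry, mean follow-up at the end of December 2025 is 0.25 years, so about 210 × 0.25 × 0.034–0.037 = 1.8–1.9 progression events would have occurred. Validation-cohort recruitment runs to May 2026 (section 9), by which time only about 5 would be expected in the modelling cohort.

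**The case against.** The strongest objection is that the 30 in section 5.4 are patients with adverse prognosis events, and elsewhere the protocol uses adverse prognosis more widely. Section 3.2.1 models it with all-cause death and MACE, and section 3.1(3) lists cardiac death and MACE as secondary end points. Eight to twelve further patients with such events would close the gap. This stands as a limit on the claim: the shortfall is shown for progression only. It does not rescue the calculation, because 5.4 uses only the progression count, does not define the wider group and gives no rate for it.

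The figure of about 20 also assumes a roughly constant hazard, that the cited risk carries over to these inpatients, and that the cited outcome matches the protocol's definition. None of these can be verified from the protocol. The ranges above cover the first. For the second, a hazard about 1.4–1.7 times the cited one would be needed, and the protocol offers no support for that.

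Section 5.5(4) does not restrict the comparison to the modelling cohort. Pooling all 270 narrows the gap considerably, with P(≥30) at 24–41%, or 10–20% after 10% loss. The mean still falls short of 30, and 5.4 derives 210, not 270, from the 30-event requirement.

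Regular adequacy assessments are mentioned without a rule or a trigger, and the adjustment sentence ties changes to recruitment speed and data quality. Neither addresses an event shortfall that would become visible only long after recruitment ends.

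Finally, the study is labelled exploratory and states no power. That limits the consequence to precision, but 5.4 words the 30 as a requirement.

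**Conclusion.** The concern holds. The protocol's arithmetic reproduces, but it delivers 30 progression events only if the 4.7-year proportion is reached within 3 years. At the cited rate and a constant hazard, the expected count is about 61–66% of target with 189 evaluable patients and 68–74% with 210. It remained below 30 in every sensitivity case examined. The cost is a standard error some 14–23% larger than with 30 events; no loss of power is claimed. The conclusion assumes that the cited cohort's risk and outcome definition apply here, and it is confined to DKD progression. Because 30 is the sole stated basis for the modelling cohort, section 5.4 must be corrected.

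**What to change.** Replace the unconverted calculation and the 30-event requirement in section 5.4 in one edit, by one of two routes.

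1. State the yield that 210 is expected to give, and delete the requirement of 30 per group and 30 events. Suggested wording:

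> The cited study recorded 156 progression outcomes among 975 patients over a mean of 4.7 years (16%). Under a constant hazard, and if its outcome definition and risk carry over to this cohort, that is about 10% at 3 years. With 210 enrolled and 10% lost, some 18–20 patients with DKD progression are expected (20–22 with no loss). For this comparison the adverse-prognosis group is defined by the primary end point and is expected to contain about 20 patients; the comparison is exploratory and less precise than one with 30.

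2. Keep 30, define adverse prognosis in 5.4 by the wider set of events intended, and cite a documented 3-year risk of about 16% for that definition (14% if no loss is assumed). Describe 30 as an expected count, since at 16% of 189 the chance of reaching it is only about 55%.

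Either route is a text change in 5.4, with no new patients, visits or assays. The cost of the first is a less favourable stated event count. For scale only, 30 progression events in 3 years would need about 30/0.1053 = 285 to 30/0.0971 = 309 evaluable patients, or 317–344 enrolled with 10% loss. That enlargement is not proposed.

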#### **(5) Construction and Evaluation of Forecasting Model**

First, feature screening was performed using LASSO regression to select variables from five aspects: demographic characteristics, baseline scales, gut microbiota and non-target metabolites, and peripheral blood inflammatory biomarkers. Nine machine learning algorithms were employed to construct classification models, with performance evaluated through resampling training/verification mechanisms. The optimal model was selected via 10-fold cross-validation and performance metrics. Model performance and applicability were assessed using AUROC curves, calibration curves, Brier scores, and decision analysis plots. During training, validation, and testing phases of the optimal model, five-fold cross-validation and learning curves were used to evaluate model fit and stability. Finally, SHAP package was utilized to generate SHAP explanation plots to determine the importance and contribution of individual features.

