Based on baseline data, gut microbiota, serum metabolites, and inflammatory factors, predictive models will be constructed using machine learning algorithms (e.g., random forests, support vector machines, neural networks). Feature selection methods (e.g., LASSO regression, recursive feature elimination) will be employed to identify the most prognostic features, thereby enhancing model accuracy and interpretability. Internal stability of the models will be assessed through 10-fold cross-validation, while their generalization ability will be validated using independent validation cohorts.

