January 2029-July 2029	
Main content of the stage goal:
 
① Clinical Validation of the Model: Validate the predictive model using additional recruited patients to evaluate its practical value and feasibility in real-world clinical settings. Based on validation results, make necessary adjustments and improvements to the model. This will facilitate its clinical application and promote its adoption, providing scientific evidence for prognostic assessment and personalized treatment of diabetic kidney disease (DKD) patients. The process will culminate in the completion of a clinical validation report.
 
② Complete the project: write the paper and complete the project report. Results:
 
 
① The clinical validation report was completed.
 
② The final report was completed, and the relevant academic papers were written and published.
 

------------------------	--

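### The 60-patient validation cohort has no stated basis; for DKD progression it would yield about 6 events at 3 years, too few to support the validation claims

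*Protocol*

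**What the plan says.** Section 5.4 sizes the modelling cohort from an event rule: "meaning there must be at least 30 patients with adverse prognosis events". The rate comes from a published cohort that "included 975 DKD patients with an average follow-up of 4.7 years, reporting 156 major outcomes of DKD progression". The calculation is "975/156*30=187.5", raised for dropout to 210. The next sentence is "Additionally, 60 DKD patients were included as a validation cohort". No event target, precision target or other reason for 60 follows.

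Follow-up in this study is shorter than in the cited cohort. Section 5.5(3) gives "follow-up time: 3 years after discharge".

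The 60 patients carry a heavy task. Section 5.8.2 says of the models that "their generalization ability will be validated using independent validation cohorts". The January to July 2029 stage in section 9 reads "Validate the predictive model using additional recruited patients to evaluate its practical value and feasibility in real-world clinical settings", and goes on to adjustment of the model and its clinical adoption. Section 5.5(5) describes LASSO screening as the first step, then "Nine machine learning algorithms were employed to construct classification models", with the best one picked by 10-fold cross-validation. The performance measures there are AUROC, calibration curves, Brier score and decision analysis.

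**The concern.** Apart from resampling within the modelling data, the 60 later patients are the only check the protocol names on a model built by LASSO screening of microbiome and untargeted metabolite data and then selected from nine algorithms. With so few events behind that search, optimism is a real danger, and the validation cohort ought to expose it.

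The information in a validation cohort depends mainly on its number of events. If that number is in single figures, a good result may be luck and a poor result may be bad luck. A report that the model generalizes and has practical value would then rest on an estimate that cannot separate a moderately useful model from a nearly useless one. Section 9 also allows the model to be adjusted after the validation result is known, and the adjusted model would have no independent test at all.

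**Working it through.** **Inputs.** 975 patients, 156 progression outcomes, mean follow-up 4.7 years, 30-event target, 210 modelling and 60 validation patients, 10% dropout (all section 5.4); 3 years of follow-up (section 5.5(3)); total 270 (section 5.3.2).

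**The plan's own figure.** 156/975 = 0.16, and 30/0.16 = 187.5, which reproduces exactly. With 10% dropout, 187.5/0.9 = 208.3 and 187.5 × 1.10 = 206.3, both close to 210. There is no corresponding figure to reproduce for the 60.

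**Expected progression events among 60.**
- Unadjusted 16%: 60 × 0.16 = 9.6.
- Person-time rate: 0.16/4.7 = 0.0340 per year; 1 − exp(−3 × 0.0340) = 9.7% at 3 years; 5.8 events.
- Linear scaling: 0.16 × 3/4.7 = 10.2%; 6.1 events.
- Constant hazard from the proportion: 1 − 0.84^(3/4.7) = 10.5%; 6.3 events.
- After 10% dropout (54 patients), the three 3-year figures become 5.2, 5.5 and 5.7, and the unadjusted figure becomes 8.6.

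**Spread of the count (binomial, n = 60).** At 9.7% to 10.5% the 95% range is 2 to 11 events, and the chance of 4 or fewer is 0.30 to 0.23. At 16% the range is 4 to 15.

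**Discrimination.** Hanley–McNeil variance for AUROC A with m events and n non-events: [A(1−A) + (m−1)(K1−A²) + (n−1)(K2−A²)]/(mn), where K1 = A/(2−A) and K2 = 2A²/(1+A). An AUROC of 0.75 is an assumption, since the documents give none; K1 = 0.600, K2 = 0.643, A² = 0.5625.
- m = 6, n = 54: (0.1875 + 0.1875 + 4.259)/324 = 0.01430; SE 0.120; 95% CI 0.52 to 0.98.
- m = 10, n = 50: (0.1875 + 0.3375 + 3.9375)/500 = 0.00893; SE 0.094; 95% CI 0.56 to 0.94.
- Range of assumed AUROC with 6 events: 0.46 to 0.94 at 0.70, and 0.65 to 1.00 at 0.85.

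**Calibration.** For observed over expected events, the SE of the log ratio is √((1 − e/60)/e). With e = 6.3 it is 0.376, so the 95% CI spans a factor of 0.48 to 2.1. With e = 9.6 it is 0.296, a factor of 0.56 to 1.8. The calibration slope was simulated for a perfectly calibrated model in cohorts of 60 with about 10% events. With a linear-predictor SD of about 1, 95% of the estimated slopes lie between about 0.0 and 2.8. The range depends on that assumed SD, but it stays very wide for SDs from 0.5 to 2.

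**Association analyses.** At 9.7% to 10.5%, 210 patients give 20.4 to 22.1 events at 3 years and 270 give 26.2 to 28.4, a gain of 270/210 − 1 = 29%.

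**The case against.** Section 5.4 calls the study exploratory and allows the sample size to be adjusted. Cross-validation is already planned, and a small later cohort reported with confidence intervals is a legitimate supplement. All of that stands, but it does not rescue the claims. The adjustment clause rests on recruitment speed and data quality and sets no event target for validation. Sizing validation by events instead would be costly: even 30 events would need 30/0.1053 = 285 patients at the 3-year rate.

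It is also fair to say that discrimination is not wholly beyond judgement. With 6 events, a true AUROC of 0.50 gives 0.25 to 0.75 and one of 0.90 gives 0.73 to 1.00, which barely overlap. The cohort could tell a worthless model from an outstanding one, but not from a moderately good one.

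A reader might infer that the 60 are withheld from the main analyses and that 60/270 = 22% of the patients are wasted. The documents do not support this. The study population is 270, section 5.5(2) collects samples from all participants, sections 5.5(4) and 5.8.2 restrict no association analysis to one cohort, and the 60 come on top of the 210. Separation is only suggested, by the 30-event rule being met from the 210 alone and by the association analysis being scheduled for 2028. The accurate statement is that the protocol does not say whether the 60 enter.

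A reader might also take 9.6 events at 16% as a guarantee of fewer than 10. It is an expectation: at that rate, the chance of fewer than 10 is 0.50.

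**Conclusion.** The size of 60 is fixed in the protocol without an event or precision basis. For DKD progression it would bring about 6 expected events at 3 years, and 9.6 without adjustment for the shorter follow-up. At either count the estimates of discrimination and calibration are too imprecise to support validated generalization or real-world practical value, so the conclusion does not hang on how the rate is scaled to 3 years.

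The counts assume that the cited cohort's rate and end point carry over to these patients, and that the model predicts DKD progression. Section 3.2.1 names all-cause death as the model's primary end point; without a death rate in the documents, nothing can be said about the number of validation events for it. The view of the 60 as a later cohort rests on the January to May 2026 recruitment in section 9. Section 5.3 places recruitment in July to December 2025 and gives a population of 270, so these dates need reconciling.

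**What to change.** 1. In sections 5.5(5) and 5.8.2, make optimism-corrected internal validation the main performance estimate. Repeat the whole pipeline (LASSO screening, tuning and choice among the nine algorithms) within each resample of the modelling cohort.
2. Freeze the model developed on the 210 and apply it once to the 60 as a descriptive temporal check, before any refit or adjustment. Report the number of events and 95% confidence intervals for AUROC, calibration and Brier score. Label any model later adjusted, or refitted on all 270, as internally validated only. The order matters, because a model trained on all 270 has no independent check in the 60.
3. Replace the claims in section 5.8.2 and in the 2029 stage of section 9 with 'internally validated, with an exploratory temporal check'.
4. State that the 60 also enter the association analyses of sections 3.1 and 3.2.2 once their follow-up is complete. Expected 3-year events rise from about 20–22 to 26–28, still short of the protocol's own minimum of 30.

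Cost: no extra patients, but a weaker validation claim and more computing. Patients recruited in January to May 2026 complete 3 years in January to May 2029, so association analyses on all 270 finish in the first half of 2029 instead of 2028, close to the project's end in July 2029.
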